- e. Participants who discontinue study intervention early will have an early WD visit and will enter follow-up unless they withdraw consent. Participants who withdraw consent will be offered an optional safety follow-up visit to occur on the day of consent withdrawal. For the optional safety follow-up visit, assessments are at the investigator's discretion and could be similar to the early WD visit.
- f. Both the Platform Master ICF and the ISA ICF must be signed before the first study-related activity. For participants who consent to participation in the intensive PK study (optional), the corresponding checkbox in the ISA ICF must be checked.
- g. Minimum criteria for the availability of documentation supporting the eligibility criteria are described in the source documents section in Attachment 3 of the Master Protocol PLATFORMPAHPB2001. Clinical status will be checked and documented at screening and again before first dose of study intervention. If a participant's clinical status changes (including any available laboratory results or receipt of additional medical records) after screening but before the first dose of study intervention is given such that he or she no longer meets all eligibility criteria, then the participant should be excluded from participation in the study.
- h. Medical history also includes mode of HBV transmission, stage of liver fibrosis, and alcohol consumption. Historical HBV DNA, ALT, HBsAg, and HBeAg data, if available, will be recorded in the CRF and/or source documents. Available historical data on previous HBV genotype assessments will also be collected in the CRF. HBeAg status should also be recorded.
- i. Liver disease staging assessments will be performed based on Fibroscan or liver biopsy results, obtained within 6 months prior to screening or at the time of screening (in case of Fibroscan) or within 1 year prior to screening (in case of liver biopsy).

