Note: In case of ALT elevation $\geq 3x$ ULN at Week 24, the investigator must consider different potential causes of increased ALT to ensure appropriate work up and management as needed. If the ALT elevation is unrelated to HBV activity and/or $<3x$ ULN by FU Week 2, NA completion may be considered at the discretion of the investigator and in consultation with the sponsor.

Participants who do not meet the above criteria at Week 24 should continue NA treatment during the 48-week FU Period.

If a participant prematurely discontinues investigational intervention before Week 24, follow-up assessments should be obtained as per the [Schedule of Activities](#) until 48 weeks after the end of investigational intervention unless the participant withdraws consent. In this case, NA treatment may be continued or, in consultation with the sponsor, discontinued, based on the above-mentioned NA treatment completion criteria.

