5.1.1. Analysis Phase

The analysis phases are defined in [Table 3](#) below.

Table 3: Analysis Phases Start and End Dates

Analysis Phase	Start date	End date
Screening	The date of signing the informed consent	1 day before the first study agent intake (excluding PegIFN- α 2a)
Treatment Period 1	Date of first study agent intake (excluding PegIFN- α 2a)	For participants who receive PegIFN-α2a: Min [Date of first PegIFN- α 2a intake - 1 day, cut-off date ^b]
		For participants who do not receive PegIFN-α2a: Date of Week 12 study agent intake - 1 day
		For participants who discontinue treatment before Week 12: Max [last intake date of any study agent, study agent discontinuation date, early study withdrawal visit date] + 5 days ^a or cut-off date ^b , whichever occurs first
Treatment Period 2	For participants who receive PegIFN-α2a: Date of first PegIFN- α 2a intake	For participants who did not withdraw from the study prior to the projected/actual Week 24 visit date: Max [last intake date of any study agent, study agent discontinuation date, projected/actual Week 24 visit date] + 5 days ^a or cut-off date ^b , whichever occurs first
	For participants who do not receive PegIFN-α2a: Date of Week 12 study agent intake	
	Otherwise: missing	
Follow-up	Participants who did not withdraw informed consent during treatment period 1 or 2: Max [End date of Treatment Period 1, End date of the Treatment Period 2] + 1 day	Max [study discontinuation date, study completion date] or cut-off date ^b , whichever occurs first
	Otherwise: missing	Otherwise: missing

^a Addition of 5 days is only applicable for Adverse Events and Concomitant Medications.

^b Cutoff dates will be defined to match the prespecified timepoints for DRC safety monitoring, interim analyses, the primary and final analyses, respectively.

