5.1.2.3. Follow Up Relative Day

Follow Up (FU) start date (FU Day 1) is defined in [Table 3](#). Efficacy and safety assessments during the FU phase will be assigned a day relative to this date. The FU study day in the FU phase (ADY) is defined as:

$$FU\ ADY = \text{visit date} - FU\ \text{start date} + 1$$

for visits on or after FU Day 1.

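### SAP Table 3 dates follow-up from the projected Week 24 visit for participants who stop study agents in Treatment Period 2 but stay in the study, while the protocol dates it from the actual stop, so their follow-up visits get the wrong week labels

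*SAP*

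**What the plan says.** **Protocol.** A participant who stops early still gets a full follow-up. Schedule of Activities footnote e: "Participants who discontinue study intervention early will have an early WD visit and will enter follow-up unless they withdraw consent". Section 6.6 sets its length: assessments continue "until 48 weeks after the end of investigational intervention unless the participant withdraws consent". Section 4.1 agrees, and the Schedule places Week 24, end of study intervention and the withdrawal visit in one column, from which follow-up visits are counted.

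**SAP Table 3.** For discontinuation before Week 12, Treatment Period 1 ends at "Max [last intake date of any study agent, study agent discontinuation date, early study withdrawal visit date", so the actual stop governs. The Treatment Period 2 row applies "For participants who did not withdraw from the study prior to the projected/actual Week 24 visit date" and ends the period at "Max [last intake date of any study agent, study agent discontinuation date, projected/actual Week 24 visit date". The extra 5 days in both rows applies only to adverse events and concomitant medications. Follow-up starts at "Max [End date of Treatment Period 1, End date of the Treatment Period 2] + 1 day".

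**SAP 5.1.2.3 and 5.1.3.** "Efficacy and safety assessments during the FU phase will be assigned a day relative to this date". Table 4 then allocates visits within each phase. Week 24 exists only in Treatment Period 2 (Days 156 to 183), and FU Week 48 is FU day 324 onward.

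**The concern.** Stopping agents is not the same as leaving the study. A participant who stops at Week 14 and attends every later visit is still in the study at Week 24, so the projected date wins the maximum and the phase stays open for up to 12 weeks after the stop. Four things follow.

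- Early follow-up visits are reported as Treatment Period 2 visits, in efficacy summaries and in safety tables by phase.
- Later visits are labelled too early by the gap between the stop and Day 169, so summaries by follow-up week mix different times since stopping.
- Many of these participants have no FU Week 48 value although they completed the protocol's follow-up. Functional and partial cure are analysed mainly on observed cases (SAP 5.4.2.1.4 and 5.4.2.1.13), so they drop out of the denominator. Sustained HBsAg response, Definition 1 (SAP 5.5.1.5), then applies its alternative thresholds for missing FU Week 48 data.
- For the primary endpoint, a Day 169 HBsAg sample is a Week 24 value after a Period 2 stop. After a Period 1 stop it belongs to follow-up, so Week 24 is missing and the participant is a non-responder under SAP 5.3.2.1.1.

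**Working it through.** **Inputs.** Week 24 target: study Day 169 (SAP Table 4). Protocol FU Week *k* falls 7*k* days after the end-of-intervention or withdrawal visit (Schedule: FU Week 48 is Day 337, counting that visit as Day 1). Windows are from Table 4. I read its Treatment Period 2 intervals as days from first dose, as the targets 85 to 169 imply, and take the withdrawal visit to be on the stop day *s*.

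**Formulas.** FU Day 1 is Day 170, so SAP FU day = visit day − 170 + 1 = visit day − 169. Protocol FU Week *k* is on study day *s* + 7*k*, which is SAP FU day *s* + 7*k* − 169.

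**Check on a completer.** With *s* = 169, FU Week 48 has FU day 336, inside the window from 324. FU Weeks 2, 4, 8, 12, 24 and 36 (FU days 14, 28, 56, 84, 168, 252) also land in their own windows. The rule works for those who finish.

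**Early stops** (study day, FU day where it applies, SAP label):

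| Protocol visit | Stop Week 14 (Day 99) | Stop Week 16 (Day 113) | Stop Week 20 (Day 141) |
|---|---|---|---|
| FU W2 | 113: Week 16 | 127: Week 16 | 155: Week 20 |
| FU W4 | 127: Week 16 | 141: Week 20 | 169: Week 24 |
| FU W8 | 155: Week 20 | 169: Week 24 | 197, FU 28: FU W4 |
| FU W12 | 183, FU 14: FU W2 | 197, FU 28: FU W4 | 225, FU 56: FU W8 |
| FU W24 | 267, FU 98: FU W12 | 281, FU 112: FU W16 | 309, FU 140: FU W20 |
| FU W36 | 351, FU 182: FU W24 | 365, FU 196: FU W28 | 393, FU 224: FU W32 |
| FU W48 | 435, FU 266: FU W36 | 449, FU 280: FU W40 | 477, FU 308: FU W44 |

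The rows are the visits that remain mandatory for a stable participant on continued NA (Schedule footnote qq). After a Week 20 stop, such a participant can attend all of them and have no value labelled FU Week 12, 24, 36 or 48.

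**Who reaches FU Week 48.** The last visit is on FU day *s* + 336 − 169 = *s* + 167. It needs *s* + 167 ≥ 324, so *s* ≥ 157. With the ±4-day visit window the limit is Day 153 (visit 4 days late) to Day 161 (4 days early).

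**Share of Period 2 stoppers affected.** Stop timing is not given. If stop days were uniform over Days 85 to 168, Days 157 to 168 (12 of 84) keep an FU Week 48 value and 72/84 = 86% lose it (81% to 90% across the visit window). If all stops fell at the Week 14, 16 or 20 visits, all lose it.

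**Effect on a rate.** Assume 5 responders among 50 and 1 to 5 non-responders lost: 5/50 = 10.0% becomes 5/49 = 10.2% up to 5/45 = 11.1%.

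**With follow-up dated from the stop.** FU day = 7*k*, so FU Week 48 has FU day 336 for all 84 stop days.

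**The case against.** **The text may mean something else.** The Schedule has one column for Week 24 and the withdrawal visit, so an *actual* Week 24 visit could include a withdrawal visit, and the conflict would vanish. Or a participant with a withdrawal visit in Period 2 may fall outside the row altogether. Neither reading fits well. The Period 1 row names the withdrawal-visit date and the Period 2 row does not, and a projected date inside a maximum overrides any earlier stop. If the row does not cover these participants, Table 3 gives them no end date, which needs the same addition.

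**The rule may be deliberate.** Holding Period 2 open preserves a Week 24 HBsAg value. That is a fair motive, and the fix has to keep it.

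**Mitigation exists.** HBsAg seroclearance and HBV DNA below LLOQ are also evaluated from the actual stop (SAP 5.4.1.1.4.2 and 5.4.1.1.11), though Table 4 has no windows on that clock. The EOS time point captures the last visit. LOCF for FU Week 48 accepts FU Week 36 onward, where the last visit always lands. All of this stands, but it does not correct the observed-case summaries by follow-up week.

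**Stronger readings that the documents do not support.**
- A reader might infer that PegIFN-α2a toxicity makes the problem common. Most of the specific toxicity stops in Protocol 7.1 end PegIFN-α2a alone, and someone who continues JNJ-3989 to Week 24 is unaffected.
- A reader might call the mislabelled samples off-drug. SAP 5.1.11 extends on-treatment to 28 days after JNJ-3989 and 2 days after NA, and NA may continue. Post-discontinuation is the accurate term.
- A reader might say that FU Week 48 data can never exist. That is true of scheduled visits only: the window is open-ended, and unscheduled visits or extended follow-up after NA restart could fill it.
- A reader might expect the cure rates to be badly distorted. Functional cure requires the NA completion criteria at Week 24, and partial cure requires stopping everything including NA, so the effect is mainly on denominators.

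**Conclusion.** The inconsistency holds on the plain reading of Table 3: two kinds of early stopper run on different follow-up clocks, and the clock for Period 2 stoppers contradicts the protocol. The mislabelling is deterministic, up to about 12 weeks, and for stops before about Day 157 it removes the scheduled last visit from FU Week 48. The primary-endpoint asymmetry is also real, but it matters only where a sample is actually taken near Day 169.

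The size in this trial is unknown because neither document gives stopping rates. Each affected participant is 2% of 50, and the illustrative shift in an FU Week 48 rate is about 1 percentage point or less. The study is exploratory and descriptive with no hypothesis test, and several analyses soften the effect. This should be fixed, but it does not threaten the trial's main conclusion.

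**What to change.** 1. In Table 3, add a Treatment Period 2 row for participants who discontinue study agents in that period but stay in the study. Treatment Period 2 ends at the latest of last study agent intake, discontinuation date and early withdrawal visit; FU Day 1 is the next day. This matches the Period 1 rule and the protocol.
2. Select the value for every Week 24 endpoint by study Days 156 to 183 from first dose, regardless of analysis phase: primary endpoint, treatment failure, NA completion criteria, Week 24 change from baseline, and the Week 24 entries in Table 6. Restricting this to the primary endpoint would lose Period 2 stoppers' Week 24 values elsewhere.
3. State in SAP 5.1.3 that one sample may then carry both a Week 24 and a follow-up label, as an exception to single allocation.

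Both of the first two parts are needed; the first alone would turn Period 2 stoppers into missing Week 24 cases. If the present rule is intended, the SAP should say so and reconcile it with Protocol 6.6.

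The cost is SAP wording and a derivation change, with no new data. The downside is that a few post-discontinuation Week 24 values from Period 1 stoppers replace automatic non-response in the primary endpoint, and some samples carry two labels.

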5.1.2. Relative Day by Study Phase

An analysis relative day (ADY) will be calculated for all assessments at all visits for each participant.

5.1.2.1. Treatment Period 1 Relative Day

The treatment period 1 start date (TP Day 1) is defined as the date of the first study agent intake (excluding PegIFN- α 2a). All efficacy and safety assessments during the treatment period 1 will be assigned an analysis study day relative to this date.

The study day in the treatment period 1 phase (TP1 ADY) is defined as:

$$TP1\ ADY = \text{visit date} - TP1\ \text{start date} + 1$$

for visits on or after treatment period 1 Day 1, and

$$TP1\ ADY = \text{visit date} - TP1\ \text{start date}$$

for visits before TP1 Day 1 (Screening phase).

There is no 'TP1 Day 0'.

5.1.2.2. Treatment Period 2 Relative Day

The treatment period 2 start date (TP2 Day 1) is defined as the date of first PegIFN- α 2a injection for those who receive PegIFN- α 2a in treatment period 2, and the date of Week 12 agent intake for those who don't receive PegIFN- α 2a. Efficacy and safety assessments during the TP2 will be assigned an analysis study day relative to this date, unless otherwise specified.

The study day in the TP2 phase (TP2 ADY) is defined as:

$$TP2\ ADY = \text{visit date} - TP2\ \text{start date} + 1$$

for visits on or after TP2 Day 1.

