AFP: alpha-fetoprotein; ALP: alkaline phosphatase; ALT: alanine aminotransferase; AST: aspartate aminotransferase; CKD-EPI: Chronic Kidney Disease Epidemiology Collaboration; CRF: case report form; CT: computed tomography; D/d: day; DAIDS: Division of Acquired Immunodeficiency Syndrome; DBP: diastolic blood pressure; DNA: deoxyribonucleic acid; ECG: electrocardiogram; eGFR: estimated glomerular filtration rate; EOS: end of study; EOSI: end of study intervention; FSH: follicle-stimulating hormone; FU: follow-up; GI = giga; HBe: hepatitis B core protein; HBe(Ag): hepatitis B e (antigen); HBcrAg: hepatitis B core-related antigen; HBs(Ag): hepatitis B surface (antigen); HBV: hepatitis B virus; HCC: hepatocellular carcinoma; HIV-1 (-2): human immunodeficiency virus type 1 (type 2); HLA: human leukocyte antigen; ICF: informed consent form; IgM: immunoglobulin M; INR: International Normalized Ratio; ISA: intervention-specific appendix; MRI: magnetic resonance imaging; NA: nucleos(t)ide analog; PBMC: peripheral blood mononuclear cells; PegIFN- α 2a: pegylated interferon alpha-2a; PK: pharmacokinetic; RBC: red blood cell; RNA: ribonucleic acid; SBP: systolic blood pressure; T4: thyroxine; TSH: thyroid stimulating hormone; ULN: upper limit of normal; W: week; WD: withdrawal.

- a. All study visits are to be scheduled relative to the baseline (Day 1) visit date. All follow-up study visits are to be scheduled relative to the Week 24/EOSI visit. An unscheduled visit can be performed upon the investigator's discretion, in case of HBV DNA elevations, ALT elevations, other signs of worsening of liver disease, or for any other reason.
- b. If necessary (eg, for operational reasons), the Screening Period may be extended up to a maximum of 8 weeks in agreement with the sponsor.
- c. Day 1 samples are to be collected before the first dose of study intervention.
- d. All assessments (with the exception of the sparse and intensive PK samples) should be performed before administration/intake of JNJ-3989 and NA. If applicable, weekly PegIFN- α 2a administration should preferably be done on the same day of the week in the evening by self-injection. If desired, participants can also choose to have the administration of PegIFN- α 2a performed on site irrespective of the time of day. For participants in Japan, weekly administration of PegIFN- α 2a must be performed at the study site by the investigator or his/her designee.

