5.1.3. Visit Windows

As participants do not always adhere to the protocol visit schedule, the following rules are applied to assign actual visits to analysis visits. All visits for all assessments (safety, efficacy or PK) will

be uniquely allocated within each phase to an analysis time point based on the analysis relative day (ADY) compared with the target day based on Table 4. All assignments will be made in chronological order. Once a visit date is assigned to a visit window, it will no longer be used for a later time point except for the end of treatment period 1 (EOT1), end of treatment period 2 (EOT2), and end of study (EOS) visits. If a participant has 2 or more actual visits in one visit window, the visit closest to the target day will be used as the protocol visit for that visit window. The other additional visit(s) will not be used in the summaries or analyses, but they can be used for determination of clinically important endpoints. If 2 actual visits are equidistant from the target day within a visit window, the later visit is used. If there are two or more measurements on the same day, then the last measurement in chronological order will be used. If the time of the assessment is not available, the highest record/sequence number will be selected.

The listings will include all measurements, also those multiple assessments with the same visit window/phase. Spaghetti plots will also display all measurements.

End of treatment period 1 (i.e. EOT1), end of treatment period 2 (i.e. EOT2) and end of study (i.e. EOS) time points will be included in all analyses over time unless stated otherwise.

Table 4 provides the analysis time points and time intervals for each visit per analysis phase.

Table 4: Visit Windows

a) Screening, Treatment Period 1, and Treatment Period 2

Analysis phase	Target day	Analysis time point (Week)	Analysis time point (label)	Time interval (days)
Screening	$-\infty$	-1	Screening	<0
Treatment period 1	1	0	Baseline	Pre-dose: 1
	15	2	Week 2	[2,22]
	29	4	Week 4	[23,43]
	57	8	Week 8	[44,81]
	85 ^a	12.1	Week 12 period 1	[82, 92] ^a
	Last visit in treatment period 1	12.15 ^b	EOT1 ^b	
Treatment period 2	85 ^a	12.2	Week 12 period 2	[82, 92] ^a
	99	14	Week 14	[93,106]
	113	16	Week 16	[107,127]
	141	20	Week 20	[128,155]
	169	24	Week 24	[156,183]
	Last visit in treatment period 2	25 ^c	EOT2 ^c	

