^a Day 85 is the target day for the first administration of PegIFN- α 2a. Time interval [82-92] was selected to align the visit window with the protocol Schedule of Activities for Week 12. Any assessments performed before the administration of PegIFN- α 2a (date/time) at week 12 will be considered under treatment period 1 (Week 12 period 1) and assessments after the administration of PegIFN- α 2a (date/time) will be considered as treatment period 2 (Week 12 period 2).

^b End of treatment period 1 (EOT1) visit will be the last visit of treatment period 1.

^c End of treatment period 2 (EOT2) visit will be the last visit of treatment period 2.

b) Follow-up

Analysis phase	FU Target day	Analysis time point (Week)	Analysis time point (label)	Time interval (FU days)
Follow-up	15	26	Follow-up Week 2	[1, 22]
	29	28	Follow-up Week 4	[23, 43]
	57	32	Follow-up Week 8	[44, 71]
	85	36	Follow-up Week 12	[72, 99]
	113	40	Follow-up Week 16	[100, 127]
	141	44	Follow-up Week 20	[128, 155]
	169	48	Follow-up Week 24	[156, 183]
	197	52	Follow-up Week 28	[184,211]
	225	56	Follow-up Week 32	[212, 239]
	253	60	Follow-up Week 36	[240, 267]
	281	64	Follow-up Week 40	[268, 295]
	309	68	Follow-up Week 44	[296,323]
	337	72	Follow-up Week 48	[324, +∞]
	last visit in the study	999 ^a	EOS ^a	

^a End of study (EOS) visit (last available data during the follow-up phase) will be the last visit in the study.

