5.3.2.1.1. Missing as Non-Responder

Participants who do not have HBsAg data in the analysis window of Week 24 will be defined as non-responders.

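### The SAP restarts the day count in Treatment Period 2 but windows that period in days since first dose, so the Week 24 derivation of the primary endpoint contradicts itself

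*SAP*

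**What the plan says.** - **Treatment Period 1 (TP1) day count, SAP 5.1.2.1.** Day 1 is the first study agent intake, PegIFN-α2a excluded. "All efficacy and safety assessments during the treatment period 1 will be assigned an analysis study day relative to this date".
- **Treatment Period 2 (TP2) day count, SAP 5.1.2.2.** "The treatment period 2 start date (TP2 Day 1) is defined as the date of first" PegIFN-α2a injection, or the Week 12 intake for participants who get no PegIFN-α2a. The relative day (ADY) is visit date − TP2 start date + 1. The rule that follows is: "Efficacy and safety assessments during the TP2 will be assigned an analysis study day relative to this date, unless otherwise specified".
- **Allocation, SAP 5.1.3.** Visits for all assessments are "uniquely allocated within each phase to an analysis time point based on the analysis relative day (ADY) compared with the target day" in Table 4.
- **Table 4a, TP2 rows.** Target days are 85, 99, 113, 141 and 169. The windows are Week 12 period 2 [82, 92], Week 14 [93, 106], Week 16 [107, 127], Week 20 [128, 155] and Week 24 [156, 183]. Footnote a adds: "Day 85 is the target day for the first administration of PegIFN". The table names no day origin.
- **Table 4b (follow-up).** The columns are labelled in FU days, which agrees with the follow-up relative day in SAP 5.1.2.3.
- **Primary endpoint, SAP 5.3.2.1.1.** "Participants who do not have HBsAg data in the analysis window of Week 24 will be defined as non-responders". The observed-case sensitivity analysis (5.3.2.1.2) keeps only participants with Week 24 HBsAg data.
- **Protocol 1.3, Schedule of Activities, footnote a.** "All study visits are to be scheduled relative to the baseline (Day 1) visit date". Week 12 is study day 85 ± 2 and Week 24 is study day 169 ± 3.

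**The concern.** The first PegIFN-α2a injection is Day 1 in SAP 5.1.2.2 and Day 85 in footnote a to Table 4a. Both numbers cannot be the relative day that SAP 5.1.3 compares with the table. Because 5.1.2.2 gives TP2 its own relative day and 5.1.3 allocates within each phase by relative day, a reader who follows the text applies TP2 ADY to rows that were built on another scale.

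The primary endpoint is read through the Week 24 window, and a value outside that window is scored as failure. A windowing error therefore appears as non-response, not as visible missing data. The observed-case analysis and the by-visit TP2 summaries use the same allocation.

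**Working it through.** **1. Reproduce the table.** Counting from first dose, target day = 7 × week + 1. Weeks 12, 14, 16, 20 and 24 give 85, 99, 113, 141 and 169. These are the TP2 target days in Table 4a and the study days in the protocol schedule, so the rows are on the days-since-first-dose scale.

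**2. Apply the rule in SAP 5.1.2.2.** With TP2 starting on study day 85, TP2 ADY = study day − 85 + 1 = study day − 84. The ranges let the visit move within its protocol window (± 2 days for Week 12, ± 3 days for later visits) and the TP2 start move by ± 2 days.

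| Visit | Study day | TP2 ADY (range) | Table 4a TP2 window reached |
|---|---|---|---|
| Week 12 | 85 | 1 (1–5) | none |
| Week 14 | 99 | 15 (10–20) | none |
| Week 16 | 113 | 29 (24–34) | none |
| Week 20 | 141 | 57 (52–62) | none |
| Week 24 | 169 | 85 (80–90) | Week 12 period 2 [82, 92]; none at 80–81 |

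No scheduled visit reaches [156, 183]. A TP2 ADY of 156 is study day 156 + 84 = 240, which is 240 − 169 = 71 days after the nominal Week 24 visit.

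**3. Literal consequence.** If all 50 planned participants were on schedule, none would have HBsAg in the Week 24 window. The primary rule would give 0/50. The upper limit of the two-sided 90% Clopper-Pearson interval is 1 − 0.05^(1/50) = 0.058. The same method reproduces the SAP's own interval for 25/50, 0.376–0.624. The observed-case analysis would have n = 0.

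**4. Use days since first dose instead.** Week 12 at 83–87 lies in [82, 92], Week 14 at 96–102 in [93, 106], Week 16 at 110–116 in [107, 127], Week 20 at 138–144 in [128, 155] and Week 24 at 166–172 in [156, 183]. Every visit lands in its own window.

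**5. Test the other possible repair.** Keeping TP2 ADY and subtracting 84 from the rows gives Week 20 [44, 71] and Week 24 [72, 99]. For on-schedule participants this matches step 4. Now assume that PegIFN-α2a starts two weeks late, on study day 99. The day-169 visit has TP2 ADY 169 − 99 + 1 = 71 and falls in Week 20. With no other sample in [72, 99], that participant becomes a non-responder despite having a scheduled Week 24 sample. The two repairs therefore differ off schedule, and each participant affected moves the estimate by 1/50 = 2 percentage points.

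**The case against.** The strongest reply is that the intended scale is not in doubt. The TP2 rule allows exceptions where something else is specified. Footnote a puts the first PegIFN-α2a dose at Day 85, which cannot be a TP2 day because that dose is TP2 Day 1 by definition. Table 4a runs on from TP1 to TP2 without a break and uses the protocol's study days. Where a table is phase-relative, as in Table 4b, it says so. A reader might infer from the literal arithmetic that the trial would report 0/50 whatever the true effect. The documents do not support that. A programmer would have to disregard footnote a, file Week 24 samples under Week 12 and leave Weeks 14 to 20 empty. Week 16 and Week 24 outputs also go to the Data Review Committee before the primary analysis (SAP 5.8.3.1 and Table 10), so the fault would very probably be seen.

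This reply stands on intention and on the likely outcome. It does not remove the contradiction. No sentence exempts Table 4 from TP2 ADY, and 5.1.3 sends the reader back to the relative day within each phase. Table 4b also cuts both ways: it shows that phase-relative windowing is this SAP's own practice in follow-up. Whoever spots the problem must choose a repair that the SAP does not state, in an open-label study, and step 5 shows that the choice can change responder status.

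**Conclusion.** The point holds as a contradiction in how the primary endpoint and the by-visit TP2 summaries are derived. The rule as written misplaces every scheduled TP2 visit, so this is more than a missing detail. The expected effect on the reported response rate is nil if the programs use days since first dose, as footnote a implies.

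A reader might also infer that every Week 24 and TP2 output is affected. That goes too far:
- The LOCF sensitivity analysis (SAP 5.3.2.1.3) searches within 4 weeks of the Week 24 visit and could recover the sample.
- The NA completion proportion is summarised at the end of Treatment Period 2 (5.4.2.1.2). The EOT2 record is the last visit of the period, whatever its day number.
- Adverse events of special interest are summarised by phase (5.6.2). Worst-case laboratory, ECG and vital-sign results are derived within each phase and include unscheduled assessments (5.6.3). None of these needs a visit window.

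The TP1 and follow-up windows agree with their own day counts. The literal result in step 3 assumes visits close to the protocol schedule. With TP2 starting on day 85, only a Week 24 visit at least 71 days late would escape it.

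**What to change.** State in SAP 5.1.2.2 and 5.1.3 that visit windowing in both treatment periods uses days from TP1 Day 1 (TP1 ADY). Label the target-day and interval columns of Table 4a as days from TP1 Day 1. Keep TP2 ADY only for displays relative to the PegIFN-α2a start.

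Do not re-express the TP2 rows in TP2 days. The protocol schedules treatment visits from baseline, and step 5 shows that TP2-based windows can move the Week 24 visit of a late PegIFN-α2a starter into Week 20.

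The cost is a sentence in each of two sections and a column label, with no change to data or design. Check that the programming specification already uses TP1 ADY for these rows. If it does, no output changes.
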